Objectives	
 a. Assess the safety and tolerability of F-652 in patients with alcoholic hepatitis as determined by absence of unexpected serious adverse events up to Day 42 or Day 56 following administration of first dose of study drug. b. Determine the pharmacokinetics (PK) and pharmacodynamics (PD) of F-652 in patients with alcoholic hepatitis. c. Assess the efficacy signals of F-652 in patients with alcoholic hepatitis (compared to historical patient data) as determined by : 
 A. Clinical: improvement in clinical status B. Biochemical: Improvement in liver biochemistry, MELD and Lille scores at days 7, 28, 42 and 56. C. Biomarkers of IL 22 activity (CRP, SAA, triglycerides),
Number of Subjects	Up to 18 participants at approximately six sites.

CONFIDENTIAL

This material is the property of the Mayo Clinic. Do not disclose or use except as authorized.

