Statistical Methodology	
Detailed methodology for summary and statistical analyses of the data collected in this trial will be documented in a Statistical Analysis Plan, which will be implemented by the Indiana University Data Coordinating Center. This document will expand upon and may modify the plans outlined in the protocol; however, any major modifications of the primary endpoint definition and/or its analysis will also be reflected in a protocol amendment. In this cohort dose escalation study all statistical tests will be two-sided with no adjustment for multiplicity.
 
Descriptive summaries of variables will be provided where appropriate. For continuous variables, the number of non-missing values (n) and the median, mean, standard deviation, minimum, and maximum will be summarized. For categorical variables, the number and percent of each variable will be summarized. All collected data will be presented in listings.

1 Introduction

This document is a protocol for a human research study. This study will be carried out in accordance with the applicable United States government regulations and Mayo Clinic research policies and procedures. The described study will be conducted in compliance with the protocol, Good Clinical Practices standards and associated Federal regulations, and all applicable institutional research requirements.

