1.5 Risks/Benefits

1. Beneficial Findings:

Animal studies have demonstrated that treatment with F-652 reduces ALT/AST levels in serum and TG in liver. Treatment with IL-22 adenovirus also reduces serum ALT and liver/serum TG levels. Activation of pSTAT3 was seen at 1 hr and was undetectable at 3 hrs. IL-22 induced ALT/AST/TG decreases, however, are not seen in STAT3 (hep-/-) mice. IL-22R1 expression was up-regulated in hepatocytes of alcoholic patients and ethanol-fed mice.

2. Potential Risks:

a. Overdose risk

There has been limited human experience with F-652, either at potential clinical doses or with overdose. Treatment of overdose with F-652 should consist of general supportive measures. If the symptom or sign is judged as a severe disease or disorder, treatment will be administered as per standard of care. There is no known specific antidote for overdose with F-652.

b. Warnings, precautions

There are dose-dependent increases in C reactive protein (CRP) and fibrinogen (FIB) following IV dosing with higher doses of F-652 (30 and 45 µg/kg), commencing at 12-24 hours post-dose. FIB reaches a peak at 96-120 hours post-dose; CRP may reach a peak at 48-72 hours post-dose, returning to normal 2 weeks later.

c. Hypersensitivity

The risk of hypersensitivity reactions to F-652 is unknown. If a significant hypersensitivity reaction occurs, no further doses of F-652 will be administered to that patient and appropriate treatment initiated.

d. Laboratory abnormalities

Increased serum CRP and FIB levels may be observed; these increases will be documented.

e. Local reactions at the injection site

Local injection site reactions such as erythema, dry skin and nummular eczema have occurred after the investigational product was administrated by subcutaneous injection. These changes were seen following intravenous administration at the highest dose (45 ug/kg). Local reactions generally occurred 10 to 17 days after administration of F-652, are usually were mild to moderate. Some subjects required treatment with Elocon (mometasone furoate) 0.1% cream, a moderate to strong topical corticosteroid for their skin reactions.

f. Drug interaction

The potential for drug-drug interactions with F-652 is not known.

g. Pregnancy

Adequate contraceptive methods should be used during treatment with F-652.

h. Geriatric use

There has been no geriatric experience to date.

Since no clinical data is available for F-652; any related SAE will be considered as unexpected.

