1.9 Power Calculation

As the primary outcome is observational, we have powered this study based upon the efficacy outcome, which is defined as a biochemical signal for success if AST/ALT is reduced by at least 30% on treatment. With no treatment, approximately 15-20% of patients reach this outcome following study drug treatment. We anticipate that a minimum of 50% will achieve this outcome. Using a conservative 2-sided assessment of superiority (50% with outcome vs. 20%), we will require 22 subjects to reach 80% statistical power.

For our efficacy outcome of AST/ALT, our primary analysis will assess a binary outcome of at least 30% reduction when on treatment. We will evaluate this with a 95% confidence interval of the percentage of subjects who have at least 30% reduction in AST/ALT on treatment, using an exact binary confidence interval. As a secondary analysis, we will use

CONFIDENTIAL

This material is the property of the Mayo Clinic. Do not disclose or use except as authorized.

robust linear regression with the change in AST/ALT at follow-up as compared to baseline as the outcome variable and baseline AST/ALT as the predictor. We will pair this analysis with a Bland-Altman plot. The goal of the secondary analysis is to assess the degree to which the reduction in AST/ALT attributable to treatment changes according to the subject's baseline AST/ALT. We will use 2-sides 5% type I error rate throughout.

2 *Study Objectives*

Primary:

- Assess the safety and tolerability and find the MTD of F-652 in patients with alcoholic hepatitis as determined by:
 - a. Absence of unexpected serious adverse events and,
 - b. Absence of worsening of alcoholic hepatitis (as determined by increase in MELD score > 5) up to Day 56 following administration of first dose of study drug.

Secondary:

- Determine the pharmacokinetics (PK) and pharmacodynamics (PD) of F-652 in patients with alcoholic hepatitis.

Additional:

- Assess the efficacy signal of F-652 in patients with alcoholic hepatitis as determined by:
 - a. Clinical: improvement in clinical status
 - b. Biochemical: Improvement in liver biochemistry, MELD and Lille scores at days 7, 28, 42 and 56
 - c. Biomarkers of IL 22 activity (CRP, SAA, triglycerides)

2.1 **Trial Design:**

The following study evaluations will be performed during the course of the Screening period (Day -3 to Day 0):

- Signed informed consent

CONFIDENTIAL

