2.3 Primary Study Endpoints/Secondary Endpoints

Primary:

- Absence of unexpected serious adverse events.

Secondary:

- Pharmacokinetics (PK) and pharmacodynamics (PD) of F-652 in patients with alcoholic hepatitis.

Efficacy Signal endpoints:

- Decrease in MELD score, Lille score, triglyceride, CRP, AST, ALT and SAA1

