6.3 Adverse Event Reporting

Definitions

Unanticipated Problems Involving Risk to Subjects or Others (UPIRTSO)

Any unanticipated problem or adverse event that meets the following three criteria:

CONFIDENTIAL

This material is the property of the Mayo Clinic. Do not disclose or use except as authorized.

- **Serious**: Serious problems or events that results in significant harm, (which may be physical, psychological, financial, social, economic, or legal) or increased risk for the subject or others (including individuals who are not research subjects). These include: (1) death; (2) life threatening adverse experience; (3) hospitalization - inpatient, new, or prolonged; (4) disability/incapacity - persistent or significant; (5) birth defect/anomaly; (6) breach of confidentiality and (7) other problems, events, or new information (i.e. publications, DSMB reports, interim findings, product labeling change) that in the opinion of the local investigator may adversely affect the rights, safety, or welfare of the subjects or others, or substantially compromise the research data, **AND**
- **Unanticipated**: (i.e. unexpected) problems or events are those that are not already described as potential risks in the protocol, consent document, not listed in the Investigator's Brochure, or not part of an underlying disease. A problem or event is "unanticipated" when it was unforeseeable at the time of its occurrence. A problem or event is "unanticipated" when it occurs at an increased frequency or at an increased severity than expected, **AND**
- **Related**: A problem or event is "related" if it is possibly related to the research procedures.

Adverse Event

An untoward or undesirable experience associated with the use of a medical product (i.e. drug, device, biologic) in a patient or research subject.

Serious Adverse Event

Adverse events are classified as serious or non-serious. Serious problems/events can be well defined and include:

- death
- life threatening adverse experience
- hospitalization
- inpatient, new, or prolonged; disability/incapacity
- persistent or significant birth defect/anomaly

and/or per protocol may be problems/events that in the opinion of the sponsor-investigator may have adversely affected the rights, safety, or welfare of the subjects or others, or substantially compromised the research data.

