- B. **Suspected Adverse Reaction:** any adverse event for which there is a reasonable possibility that the drug caused the adverse event. For the purposes of IND safety reporting, ‘reasonable possibility’ means there is evidence to suggest a causal relationship between the drug and the adverse event. A suspected adverse reaction implies a lesser degree of certainty about causality than adverse reaction, which means any adverse event caused by a drug.
- C. **Adverse Reaction:** any adverse event caused by a drug. Adverse reactions are a subset of all suspected adverse reactions where there is reason to conclude that the drug caused the event.
- D. **Unexpected:** An adverse event or suspected adverse reaction is considered “unexpected” if it is not listed in the investigator brochure or is not listed at the specificity or severity that has been observed; or, if an investigator brochure is not required or available, is not consistent with the risk information described in the general investigational plan or elsewhere in the current application, as amended. For example, under this definition, hepatic necrosis would be unexpected (by virtue of greater severity) if the investigator brochure referred only to elevated hepatic enzymes or hepatitis.
- E. **Serious:** An adverse event or suspected adverse reaction is considered “serious” if, in the view of either the investigator or sponsor, it results in any of the following outcomes: Death, a life-threatening adverse event, inpatient hospitalization or prolongation of existing hospitalization, a persistent or significant incapacity or substantial disruption of the ability to conduct normal life functions, or a congenital anomaly/birth defect. Important medical events that may not result in death, be life-threatening, or require hospitalization may be considered serious when, based upon appropriate medical judgment, they may jeopardize the patient or subject and may require medical or surgical intervention to prevent one of the outcomes listed in this definition. Examples of such medical events include allergic bronchospasm requiring intensive treatment in an emergency room or at home, blood dyscrasias or convulsions that do not result in inpatient hospitalization, or the development of drug dependency or drug abuse.

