7.1 Statistical Methods

Primary endpoint (safety): The number and percentage of patients with SAE and increase in MELD score > 5 up to Day 56 following administration of first dose of study drug will be summarized by each dose level. Ninety-five percent confidence interval of the percentage will be calculated too.

Summary of adverse event will also be provided by each dose level.

Secondary endpoint: Pharmacokinetics (PK) and pharmacodynamics (PD) of F-652 in patients with alcoholic hepatitis at the first dose level (10ug/kg) and subsequent dose levels will be determined by the study sponsor using standard pharmacological tools. The total exposure (area under the curve), maximum serum concentration, time at maximum concentration, last measurable serum concentration, time at last measurable concentration, clearance, volume of distribution, elimination half-life, accumulation ratio and dose proportionality will be calculated.

Efficacy signal endpoint: The main efficacy end point is the reduction of AST/ALT or serum triglycerides. If patients show a reduction of AST/ALT or serum triglyceride by 30% at day 42, the drug shows efficacy in this patient. We will calculate the percentage of patients with efficacy (rate) and its 95% confidence interval for each dose level.

We will also use the proportion of patients with 30% change of AST, ALT from baseline to Day 3, Day7, Day14, Day 28, Day 42 and Day 56 as the dependent variable, dose level and baseline AST, ALT and other patients' characteristic at baseline as the covariates to evaluate the change (efficacy) or drug by dose level. A random intercept will be included for accommodating the correlation among the repeated measurement.

Other efficacy endpoints: Paired t-test or signed-rank test will be used to compare the level Lille score. Linear mixed-effect models will be used to analyze the MELD score, triglycerides, CRP, and SAA1 in a similar way to the AST/ALT.

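### The primary safety outcome is defined inconsistently across the Summary, Sections 2, 2.3 and 7.1, and 7.1 read literally counts only patients who have both an SAE and a MELD rise above 5

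*Combined protocol and SAP*

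**What the plan says.** The protocol states the primary safety outcome in four places.

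- **Study Summary, Objectives:** "absence of unexpected serious adverse events up to Day 42 or Day 56 following administration of first dose". MELD is not part of the safety objective.
- **Section 2, Study Objectives (primary):** two conditions joined by 'and'. The first is no unexpected SAE. The second is "Absence of worsening of alcoholic hepatitis (as determined by increase in MELD score > 5) up to Day 56 following administration of first dose".
- **Section 2.3, primary endpoint:** "Absence of unexpected serious adverse events", with no MELD component and no time window.
- **Section 7.1, analysis of the primary endpoint:** "The number and percentage of patients with SAE and increase in MELD score > 5 up to Day 56", by dose level, followed by a 95% confidence interval for a single percentage. The SAE is not restricted to unexpected events, and the interval method is not named.

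Two other places bear on this. Section 1.5 says that "any related SAE will be considered as unexpected". The Statistical Methodology entry of the Study Summary says that a separate analysis plan may modify the protocol's methods, but that "any major modifications of the primary endpoint definition and/or its analysis will also be reflected in a protocol amendment".

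**The concern.** The four statements differ on which SAEs count, whether MELD belongs to the outcome, and what the window is. No section says which takes precedence. Section 7.1 also changes the logic: Section 2 requires two absences, so its failure event is one or the other, whereas 7.1 joins two presences with 'and'. Taken at its word, 7.1 would leave out a patient who has only one of the two events. For a safety endpoint that errs in the reassuring direction, because the table can show 0% when patients have failed the stated objective.

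The definition also matters before the final table. Section 4.3 makes the move from the first to the second dose level depend on information about the primary safety endpoint, while Section 1.6 escalates on dose-limiting toxicities. Section 2 lists finding the MTD under the same two conditions. These sections need to be reconciled. This review takes no position on which escalation rule should apply.

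**Working it through.** The protocol gives no figure for the primary safety endpoint, so there is nothing to reproduce. The check is a comparison of the texts, followed by illustrations.

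**1. Logic.** Let S be an unexpected SAE and M a MELD rise above 5. Section 2 is met when (not S) and (not M). Its complement is S or M. Section 7.1 read literally counts (any SAE) and M, which is not that complement.

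**2. Side by side.**

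| Place | SAE type | MELD rise >5 | Window |
|---|---|---|---|
| Study Summary | unexpected | no | Day 42 or Day 56 |
| Section 2 | unexpected | yes, either event fails | to Day 56 |
| Section 2.3 | unexpected | no | none |
| Section 7.1 | any | yes, joined by 'and' | to Day 56 |

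**3. Effect on one dose level.** Section 1.6 plans 3 patients per level. Assumed data: patient A has an unexpected SAE only, B has a MELD rise >5 only, and C has neither. Exact (Clopper-Pearson) 95% intervals:

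- 7.1 read literally (both events): 0/3 = 0% (0 to 70.8%)
- 2.3 and Study Summary (unexpected SAE): 1/3 = 33% (0.8 to 90.6%)
- Section 2 failure (either event): 2/3 = 67% (9.4 to 99.2%)

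**4. Effect of SAE type.** Suppose A's SAE is unrelated to study drug and is classed as expected. If 7.1 meant two separate summaries, its SAE line shows 1/3. An unexpected-SAE line, as in Sections 2 and 2.3, shows 0/3. The conflict over SAE type therefore remains on that reading too.

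**5. Range (assumed rates; the protocol gives none).** If each event has probability p and the two are independent, both = p² and either = 2p − p².

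- p = 0.10: both = 1%, either = 19%. The chance of counting nobody among 3 is 0.99³ = 97% under 'both' and 0.81³ = 53% under 'either'.
- p = 0.30: both = 9%, either = 51%. The chance of counting nobody is 0.91³ = 75% and 0.49³ = 12%.

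Without independence, at p = 0.20, 'both' lies between 0% and 20% and 'either' between 20% and 40%. The two agree only when the events always coincide.

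**6. MELD baseline and last value.** Section 2.1 has MELD assessed at Screening and again on Day 1, and no baseline is named. With constructed values of 15 at Screening, 16 on Day 1 and 21 later, the rise is 21 − 15 = 6 (counts) or 21 − 16 = 5 (does not). Under the Schedule of Procedures the Day 56 visit exists only after a third dose, so the last scheduled MELD is Day 42 for two-dose patients.

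**The case against.** **The joint-event reading is not the likeliest one.** The sentence in 7.1 echoes the two-item list in Section 2 and may be shorthand for summarising each item. A reader might infer that the plan intends to count only patients with both events. The documents do not establish that intent. What stands is that 7.1 does not say it means two summaries, speaks of one percentage, and on either reading disagrees with the other sections on SAE type or on the role of MELD.

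**Section 1.5 narrows the SAE gap.** This is correct for related SAEs, which all count as unexpected. Unrelated SAEs are not covered. A reader might go further and see two rival definitions of unexpected, one in 6.3 that looks to the underlying disease ("or not part of an underlying disease") and one in the FDA definitions under 6.7. The two overlap, since 6.3 also refers to the investigator's brochure, and both serve event reporting. The gap is that no section says how unrelated SAEs are classified for the endpoint.

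**Late SAEs.** A reader might infer that 7.1 loses SAEs occurring after Day 42 in two-dose patients. It does not. Dose 2 falls on Day 7 ± 3, and Section 4.3 spaces the infusions 6 to 10 days apart. With Day 1 ± 1, dose 2 falls on Day 6 to 10, and adding the 42 days in 6.3 gives Day 48 to 52, inside the Day 56 limit. SAE follow-up does outlast the last MELD visit (Day 40 to 44) by 48 − 44 = 4 to 52 − 40 = 12 days. That is a reason to state the window by component, not evidence of lost events.

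**The effect is small.** The analysis is descriptive, the stopping rules in 6.8 do not use this percentage, adverse events are also summarised by dose level, and all data are listed. All of that stands. It does not reach the link to escalation in Section 4.3.

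**A separate analysis plan could settle it.** It could supply details such as the MELD baseline. A conflict over the primary endpoint definition lies within the protocol, and the Study Summary sends major changes of that kind to an amendment.

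**Conclusion.** The point holds and should be fixed. The primary safety outcome differs across the Study Summary and Sections 2, 2.3 and 7.1 in SAE type, in the role of MELD and in window, and 7.1's literal wording is not the counterpart of the Section 2 objective. The same three patients can give 0/3, 1/3 or 2/3. Those counts are an illustration, and the 10% to 30% event rates and independence are assumptions. Independence is doubtful, because worsening liver disease can itself lead to hospitalisation. With three patients per level the intervals overlap almost entirely, so the defect lies in what is counted, not in a shifted estimate. Because individual events remain visible, the consequence is an unclear headline result and an unclear reference point for the escalation sentence in 4.3. The documents do not show that safety events would be hidden. The unnamed MELD baseline is a missing detail to settle in the same edit.

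**What to change.** Use one definition in the Study Summary, Section 2, Section 2.3 and Section 7.1. State that the SAE component is unexpected SAEs, how unrelated SAEs are classified for this purpose, and that a MELD rise above 5 is part of the primary outcome.

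In 7.1, report by dose level the number and percentage with an exact 95% confidence interval (the type Section 1.9 already names for efficacy), separately for (a) unexpected SAE and (b) MELD rise above 5. Tabulate all SAEs alongside. If a single composite is wanted, define it as either event, not both. Separate component summaries serve Section 2 equally well and avoid merging a death with a change in a laboratory-based score.

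In the same edit, name the MELD baseline (Screening or Day 1), and note that the last scheduled MELD is Day 42 for two-dose and Day 56 for three-dose patients. Reconcile the reference to the primary safety endpoint in 4.3 with the dose-limiting-toxicity rule in 1.6.

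Cost: wording in four sections through a protocol amendment, as the Study Summary foresees, and a few more table rows. No new data are needed. The cells will be small and the intervals wide, and two-dose and three-dose patients will have been followed for different lengths of time.

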1.8 Population

Patients with alcoholic hepatitis that will be recruited for this study should meet the following criteria:

CONFIDENTIAL

This material is the property of the Mayo Clinic. Do not disclose or use except as authorized.

- a. History of heavy alcohol abuse use: >40 g/day in females and >60 g/day in males for a minimum period of 6 months
- b. Consumed alcohol within 6 weeks of entry into the study
- c. Serum bilirubin > 3mg/dL AND AST >ALT, but less than 500 U/L
- d. MELD score range between 11-28. Patients with MELD scores 11-20 will be included in the first phase and patients with MELD scores 21-28 will be recruited for the second phase and escalation phase.

Patients with alcoholic hepatitis will be enrolled at approximately six clinical sites in the US. Additional sites may be added later to help accrual. The target number of participants to complete the study is 18 (see below).

STUDY NUMBERS:	
Phase I (MELD scores 11-20):	3+3+3 = 9
Phase II (MELD scores 21-28):	3+3+3 = 9
TOTAL participants:	18

Expected duration of patient participation is as follows:

Time expected for all patients to be enrolled:

- Approximately 3 years

Duration of individual patient participation:

- Up to 56 days (3 days Screening, 7-17 days of treatment, Follow up for 42 days following first dose)
- In the Dose Expansion Cohort, subjects receive 3 doses at approximately 7 day intervals. The duration of follow up will be for 56 days following first dose, or 42 days following third dose.

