- Vital signs (blood pressure, pulse, respiratory rate, and temperature) pre-dose then 3 hours post-infusion with blood pressure and heart rate monitoring every 30 minutes.
- 12-Lead ECG
- Complete physical examination, including weight and BMI
- Calculation of MELD Score
- Clinical chemistry, hematology, coagulation, lipid profile, CRP, SAA1, total protein and albumin prior to study drug dosing
- Urine pregnancy test prior to study drug dosing
- Receive third dose of study drug
- Pharmacokinetic testing
- Collection of specimens (blood and urine) for bio-specimen banking
- Nutritional Assessment

The following study evaluations will be performed during the follow-up *Day 28* (± 4 days):

- Update medical and surgical histories
- Update record of concomitant medication usage, including use of prescription and over-the-counter medications, and vitamin and/or mineral supplements
- Confirmation that patient is abstinent from alcohol
- Update Adverse Events
- Vital signs (blood pressure, pulse, respiratory rate, and temperature)
- Complete physical examination, including weight and BMI
- 12-Lead ECG
- Alcohol consumption for the last 30 days assessed using the Timeline Follow Back Questionnaire
- Calculation of MELD Score
- Clinical chemistry, hematology, coagulation, lipid profile, CRP, SAA1, total protein and albumin
- Pharmacokinetic Testing
- Immunogenicity Testing

CONFIDENTIAL

This material is the property of the Mayo Clinic. Do not disclose or use except as authorized.

- Collection of specimens (blood and urine) for bio-specimen banking.

The following study evaluations will be performed during Day 42 (± 2 days):

- Update medical and surgical histories
- Update record of concomitant medication usage, including use of prescription and over-the-counter medications, and vitamin and/or mineral supplements
- Confirmation that patient is abstinent from alcohol
- Update Adverse Events
- Vital signs (blood pressure, pulse, respiratory rate, and temperature)
- Weight and BMI
- Physical Examination
- Calculation of MELD Score
- Clinical chemistry, hematology, and coagulation
- Complete Timeline Follow-back Questionnaire
- Collection of specimens (blood and urine) for bio-specimen banking.
- Pharmacokinetic Testing
- Immunogenicity Testing
- Nutritional Assessment

The following study evaluations will be performed during Day 56 (± 2 days) (Only completed if patient received three doses of study drug):

- Update medical and surgical histories

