3.5 Data Collection and Follow-up for Withdrawn Subjects

Even though a subject has withdrawn from the study, these patients will be followed up in the hospital and to 42 days following the last administration of the study drug. Such data is important to the integrity of the final study analysis since early withdrawal could be related to the safety profile of the study drug. If a subject withdraws consent to participate in the study, for subject safety reasons, attempts should be made to obtain permission to collect follow up information whenever possible.

4 Study Drug

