Other important medical events are those that may not be immediately life threatening, but are clearly of major clinical significance. They may jeopardize the subject, and may require intervention to prevent one of the other serious outcomes noted above. For example, drug overdose or abuse, a seizure that did not result in in-patient hospitalization or intensive treatment of bronchospasm in an emergency department would typically be considered serious.

All adverse events that do not meet any of the criteria for serious, should be regarded as **non-serious adverse events**.

Adverse Event Reporting Period

For this study, the study treatment follow-up period is defined as 42 days following the last administration of study treatment.

Preexisting Condition

A preexisting condition is one that is present at the start of the study. A preexisting condition should be recorded as an adverse event if the frequency, intensity, or the character of the condition worsens during the study period.

General Physical Examination Findings

At screening, any clinically significant abnormality should be recorded as a preexisting condition. At the end of the study, any new clinically significant findings/abnormalities that meet the definition of an adverse event must also be recorded and documented as an adverse event.

Post-study Adverse Event

All unresolved adverse events should be followed by the sponsor-investigator until the events are resolved, the subject is lost to follow-up, or the adverse event is otherwise explained. At the last scheduled visit, the sponsor-investigator should instruct each subject to report, to the sponsor-investigator, any subsequent event(s) that the subject, or the subject's personal physician, believes might reasonably be related to participation in this study.

Abnormal Laboratory Values

A clinical laboratory abnormality should be documented as an adverse event after the screening visit. For this study, clinically significant laboratory abnormalities will be defined as abnormal laboratory values that in the opinion of the site investigator are not explained by alcoholic hepatitis, underlying liver disease or other underlying health conditions.

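### Sections 2 and 7.1 label the primary safety window Day 56 at every dose level, but two-dose patients have no MELD after Day 42 and no scheduled contact to the end of the adverse-event period (about Day 49)

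*Combined protocol and SAP*

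**What the plan says.** **Primary window.** The primary objective in section 2 includes no worsening of alcoholic hepatitis, "as determined by increase in MELD score > 5) up to Day 56 following administration of first dose of study drug". Section 7.1 tabulates patients with SAEs and with "increase in MELD score > 5 up to Day 56 following administration of first dose of study drug" by dose level, with a 95% confidence interval. Neither section distinguishes two doses from three. Section 2.3 lists only "Absence of unexpected serious adverse events" as the primary endpoint, with no MELD component and no window.

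**Visits.** Section 2.1 limits the Day 56 visit: "Only completed if patient received three doses of study drug". Footnote 6 of the Schedule of Procedures says the same. Section 5.2 has MELD calculated at visits.

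**Length of follow-up.** Section 1.8 gives two-dose patients "Follow up for 42 days following first dose". For the Dose Expansion Cohort it says: "The duration of follow up will be for 56 days following first dose, or 42 days following third dose". The Study Summary (Day 42 or Day 56) and section 1.6 (42 or 56 days) both allow for two lengths.

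**Adverse-event period.** Section 6.3 states that "the study treatment follow-up period is defined as 42 days following the last administration of study treatment". For withdrawn patients, section 3.5 adds that "these patients will be followed up in the hospital and to 42 days following the last administration of the study drug", and section 3.4 provides a phone call 30 days after the last assessment. Under section 6.4, active questioning about adverse events happens at contacts with the subject.

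**The concern.** Two things do not line up.

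First, a MELD rise in Days 43–56 cannot be seen in a patient who received two doses. Followed literally, 7.1 reports one percentage per dose level under a Day 56 label for patients mostly observed to Day 42. If third doses are given, they are given at the MTD, so that level may mix 42-day and 56-day patients in one denominator.

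Second, 6.3 counts its 42 days from the last dose, while the two-dose schedule in 1.8 counts its 42 days from the first. A two-dose completer therefore leaves scheduled observation before the protocol's own adverse-event period ends, although three-dose and withdrawn patients are followed for all of it. Completing the two-dose regimen should not mean less post-dose safety follow-up than withdrawing from it.

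At stake is what the primary safety result may claim: for how long each patient was observed, and whether late events were asked about or merely not volunteered.

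**Working it through.** **Inputs.** First dose Day 1. Second dose Day 7 ± 3 (schedule), with infusions 6–10 days apart (4.3). Third dose, if given, nominally Day 14. Last visit Day 42 ± 2 for two doses and Day 56 ± 2 for three. Adverse-event period = last dose + 42 days (6.3). Planned N = 18, in six cohorts of 3 (1.6, 1.8). Day labels are treated as day counts, as 1.8 itself does.

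**1. Reproduce the plan's own figure.** Three doses: 14 + 42 = Day 56. This matches the Day 56 visit and the equivalence stated in 1.8, so the three-dose schedule and 6.3 agree nominally.

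**2. Apply the same rule to two doses.**
- End of adverse-event period: 7 + 42 = Day 49.
- Last scheduled contact: Day 42.
- Follow-up after the last dose: 42 − 7 = 35 days, against 56 − 14 = 42 days with three doses.
- Uncovered: 49 − 42 = 7 days, or 7/42 = 17% of the period.

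**3. Effect of the windows on that gap.**
- Both dosing limits applied together: second dose Day 7–10, period ends Day 49–52, last visit Day 40–44. The gap runs from 49 − 44 = 5 to 52 − 40 = 12 days.
- Day 7 ± 3 alone: period ends Day 46–52, so the gap is 46 − 44 = 2 to 52 − 40 = 12 days.
- The 6–10 day interval alone: period ends Day 49–53, so the gap is 49 − 44 = 5 to 53 − 40 = 13 days.
- The nominal 7 days is the figure to use. The gap is positive under every reading.

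**4. MELD window.** 56 − 42 = 14 days without a MELD (12 to 16 with the ± 2 visit window), and 14/56 = 25% of the stated window.

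**5. Patients affected.**
- Third dose to the final cohort of 3 only (1.6, 4.3): 18 − 3 = 15.
- No third dose given: 18.

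**6. What still reaches the study after Day 42.** In two-dose completers a later MELD rise does not, because no MELD is taken. New adverse events do so only through the patient's own report of events believed related to participation (6.3), or through the rule on possibly related SAEs arising after the study period (6.4). Neither route involves a scheduled question.

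**The case against.** **The intended window can be inferred.** The Study Summary, 1.6, 1.8 and the visit schedule all point to Day 42 for two doses and Day 56 for three, so Day 56 in sections 2 and 7.1 may be meant as an outer limit. That is probably right, and it makes this a failure of alignment, not of design. It does not remove the problem. Sections 2 and 7.1 state the objective and its analysis, and they do not carry the distinction. Section 7.1 names Day 42 for efficacy and Day 56 for safety, and section 2.6 describes follow-up to Day 56 without limiting it to three doses. The Study Summary defers detail to a separate analysis plan, which is not in the text supplied. It also asks that major changes to the primary endpoint definition be reflected in a protocol amendment, so the correction belongs in the protocol.

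**Escalation does not depend on it.** This stands. Because 4.3 awaits information on the primary safety endpoint, a reader might infer that escalation is blocked or invalid. The documents do not support that: 1.6 bases escalation on DLT after the 42 or 56 days of follow-up.

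**The numerical effect is small.** This also stands. A reader might infer a serious imbalance between dose levels. With exactly 3 two-dose and 3 three-dose patients at one MTD level, the total is 3 × 42 + 3 × 56 = 294 patient-days, against 6 × 42 = 252 elsewhere, or 17% more. That needs the same MTD in both phases, no DLT expansion, no extra efficacy patients and no withdrawals. It is also minor beside exact 95% intervals of 0–71% for 0/3 or 0–46% for 0/6.

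**All nine MELD 21–28 patients might get three doses.** Section 2.4 alone could be read so, leaving 9 two-dose patients. But the Study Summary requires safety of the first two doses in that group beforehand, and 1.6 places the third dose last, after escalation. Earlier MELD 21–28 cohorts would be past Day 14.

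**A common Day 42 cut would be simpler.** It equalises calendar time but leaves three-dose patients with 42 − 14 = 28 days after the last dose, against 35 for two doses. It would move the longer follow-up of the most exposed patients out of the primary table. At the longest half-life reported in 1.4 (206 hours), 28 days is 672/206 = 3.3 half-lives and 42 days is 1008/206 = 4.9. Such a cut should not replace the regimen-specific window.

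**Late serious events are not lost altogether.** True: unresolved events are followed, and possibly related late SAEs must be reported. What remains is about a week in which new events, chiefly non-serious or seemingly unrelated ones, are not asked about.

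**Conclusion.** The point holds as an error of labelling and coverage. The Day 56 label in sections 2 and 7.1 is wrong for every two-dose patient: 15 of 18 if only the final cohort receives a third dose, 18 of 18 if none is given. The adverse-event period in 6.3 is not actively covered for two-dose completers over its last 7 days (nominal), while three-dose patients and withdrawn patients are followed for the full 42.

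It is not a large bias, and it does not invalidate DLT-based escalation. The patient counts assume the planned cohorts of three with both doses given. Expansion after a DLT, or withdrawal from dosing for a Lille score above 0.45, would change them. The 7-day gap assumes dosing and visits on their nominal days. The correction is worth making because it concerns the primary endpoint and costs little.

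**What to change.** 1. In sections 2 and 7.1, state the primary safety window by regimen: Day 42 for two doses and Day 56 for three, matching the Study Summary. Show the 7.1 summary by number of doses within dose level. A common Day 42 tabulation across dose levels may be added as a supplement, but should not replace this one.
2. For two-dose completers, add one adverse-event phone contact 42 days after the second dose (about Day 49) to section 2.1 and the Schedule of Procedures, so that the 6.3 period is actively covered.

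**Cost.** One call for each of 15 to 18 patients, with no added visits or laboratory tests. Splitting the 7.1 table by number of doses makes already small cells smaller, which the supplementary tabulation offsets. Escalation need not wait for the call.
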